9.2 SAMPLE SIZE DETERMINATION

By referencing predicate device clinical trials on respiratory rate monitoring in the hospital setting, most of the cases recruited 120+ patients. Considering a 40% withdrawal/dropout rate, we proposed a total enrollment of 300 subjects.

Details refer to the SAP.

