4.4 Endpoints

Primary Endpoint:

The difference between AirRR and ManCRR, which is greater than -3 establishes non-inferiority. The unit in this calculation is bpm and sampling rate is 1 Hz.

Secondary Endpoints:

1. The accuracy of inhalation classification in the segmentation basis is greater than 82.5% at the 95% Cl. The performance metrics (F1-socre, MAPE) at event level will be demonstrated and target for F1-score > 0.8, MAPE < 0.5.

2. To measure the agreement of AirRR and ManCRR on concordance correlation coefficient, and on their mean and bias by Bland-Altman analysis.

3. Use paired t-test to compare the response time of Airmod versus Capnography on Capnostream[™]35 after administration of jaw thrust. In the target of p<0.05 indicates significance.

4.1. The difference of ManCRR minus AirRR and ManCRR minus CapRR indicates non-inferiority at margin of 3 bpm (M1) and sampling rate 1Hz.

4.2. The difference of ManCRR minus AirRR and ManCRR minus CapRR indicates non-inferiority at margin of 2 bpm (M2) and sampling rate 1Hz.

5. The absence of unanticipated serious adverse device effect (USADE) during study period and the questionnaire.

Evaluating the Non-Inferiority of Airmod to Capnostream™35 on Respiratory Rate Monitoring and User Experience Clinical Evaluation

[Time Frame:

Non-Anesthesia Stage: Up to 40 patients will be randomly assigned to non-anesthesia stage assessment, the measurement will be evaluated after enrollment with ICF, at the non-operating room (NOR) area. (5~30 minutes)

Procedure Stage: From firstly anesthetic administration to end of procedure. (Depends on procedure 10mins ~ few hours)

Transportation Stage: During transportation of subjects. (1~10 minutes)

Post anesthesia care unit stage : From subjects arrive post anesthesia care unit (PACU) to discharge from PACU (PAR or PADSS score \geq 9) (At least 15 minutes)]

5 Study Methods

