5.1 General Study Design and Plan

This is a prospective, multi-center, pivotal study. The purpose of this study is to evaluate the noninferiority of Airmod to Capnostream^{M35} for respiratory rate monitoring. In the total of 300 subjects enrolled at the OR and NOR area in the hospital, the interim analysis will be performed at the enrollment of 150 subjects during study period. (using OBrien-Fleming to determine α =0.00153) The target population is divided into non-anesthesia, and sedative anesthesia groups. The non-anesthesia group is proposed to enroll at least 40 patients in order to indicate normal patient population in the health care facilitate. The sedative and anesthesia groups will enroll up to 260 patients to cover a wide range of health condition, comorbidity and risk of sedative patients.

Subgroup analysis is planning to indicate the induction period, intraoperative period, and PACU period. And the body mass index (BMI) will be stratified by < 30 and \geq 30 (at least 30 Number) to further examine the high risk patients group. This study will not be randomized and blinded.

Safety will be assessed by the investigator(s) and will be monitored until the end of the study. All Adverse Events (AEs) and Serious Adverse Events (SAEs) occurring during the study period will be followed until the event is considered stable or until full resolution.

The duration of this study is estimated to be 12 months, while approximately 1.5 months for each individual subject to complete all participant visits.

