7.2 Analysis Populations

(ICH E3; 9.7.1, 11.4.2.5. ICH E9; 5.2)

In our study design, both experimental and reference devices are set on all patients enrolled. The analysis is comparing the recording of devices on identical subjects. Therefore, all of the intending to treat patients are included in our study. However, if the patients were at risk of life-threatening events during their operation, the medical crew is obligated to proceed with resuscitation and stop the intervention, in such case, the recording could be terminated and the previous data is still counted in our study.

| Population | Definition / Criteria | Analyses Evaluated |
|-----------------|--|---|
| Safety | All subjects who are enrolled in the study. This population will be based on the operation the subject actually received. | Safety Adverse events/Adverse devices related events. |
| Intent To Treat | Comprise of all subjects with at least 5 minutes recording to evaluate the efficacy. This population will be based on the recording of both devices to the subjects enrolled. | Efficacy |
| Per-Protocol | The per-protocol population is a subset of the ITT population in this study. Subjects who were enrolled in the study and recorded by both devices for more than 5 minutes will be part of the ITT groups and the subjects with a protocol violation that is deemed to affect efficacy assessments in the study period, but their data will be | Per Protocol Population. |

Evaluating the Non-Inferiority of Airmod to Capnostream[™]35 on Respiratory Rate Monitoring and User Experience Clinical Evaluation

| excluded from the period(s) affected by the protocol violation for a PP analysis. (For instance, a patient who was administrated with an advanced airway management tool (LMA) should be considered as a protocol violation in the intraoperative period.) | | |
|---|--|--|
|---|--|--|

Table 3. Analysis populations

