The primary efficacy analysis of primary endpoints are comparing the difference of AirRR and ManCRR to reject the null hypothesis (difference of estimation is greater than the non-inferiority limit : -3) under 95% level of confidence interval of all ITT population. The $\mu\alpha$ denotes the respiratory counts of AirRR per minute, and the $\mu\beta$ denotes the respiratory counts of ManCRR per minute. The respiratory count per minute is the mean of recorded samples (eliminating the missing or non-detecting data

point) in each minute. Respiratory counts per minute represent the respiratory rate and are tested in the primary objective hypothesis with the type I error of 0.025, and Type 2 error of 0.2, and the power is 0.8 with single tail non-inferiority analysis.

| Step | Summary |
|-------------------------------|---|
| Objective | Non-inferiority: H0:μα-μβ> d _{NI} vs H1:μα-μβ≤ d _{NI} |
| Endpoint | Margin_1 >-3; Margin_2 >-2 |
| Error | Type I error α=0.025 (one-sided) |
| | Type II errorβ=0.2, Power 1-β=0.8 |
| Non-inferiority limit | d _N = -3 Brpm |
| Population standard deviation | σ=3.29647 |
| Others | r=1, dropout rate=0.3% |

Reference from our pilot study in 25 cases

Table 6. Statistical information referencing from pilot study

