Fig 14. Breath detection (Capnostream[™]35 & Airmod) followed by administration of jaw thrust during the apnea period

9.2.4 Analysis to compare the influence of subjects to variated breath rates on respiratory rate monitoring in bpm as measured by Airmod, manual-scored and Capnostream[™]35.

In order to determine the performance of Airmod and Medtronic Capnostream[™]35 in the ITT population, we compare them with the gold standard (ManCRR). The difference of ManCRR to AirRR and ManCRR to CapRR are parallel listed and compared to indicates non-inferiority at margin of 3 bpm (M1). The range of respiratory rate are also reported as 95% Confidence Interval of measurement. We proposed to further challenge the largest clinical acceptable range. The difference of ManCRR minus AirRR and ManCRR minus CapRR indicates non-inferiority at margin of 2 bpm (M2) are proposed to be the target of efficacy analysis.

9.2.5 Analysis to evaluate the usability of Airmod.

The demography of users will be shown in pie charts in proportion. (Recorded in [CRF_appendix 9_ Questionnaire POC] Part 1)

The evaluation of usability will be calculated from the Part 2 of [CRF_appendix 9_ Questionnaire POC], the pass rate greater than 90% showed that Airmod is good to manipulate.

10 Safety Analyses

All candidates who were subjected to the device with Airmod and CapnostreamTM35 will be included in the safety analyses (performed in the Safety population) and data will be summarized using descriptive statistics. By reporting the numbers of adverse events (AE)/serious adverse events(SAE) within the trial to indicate the incidence rate of safety issues. We will also present the total number of patients suffering from AE/SAE and its percentage of all populations.

The incidence of adverse events will be tabulated, summarized by intensity and relationship to the investigational product (IP).

• All-Cause Mortality: A table of all anticipated and unanticipated deaths due to any cause, with number and frequency of such events in each arm/group of the clinical study.

Evaluating the Non-Inferiority of Airmod to Capnostream™35 on Respiratory Rate Monitoring and User Experience Clinical Evaluation

- SAEs: A table of all anticipated and unanticipated SAEs, grouped by organ system, with number and frequency of such events in each arm/group of the clinical study. (See AEs definition below).

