- Other (Not Including Serious) AEs: A table of anticipated and unanticipated events (not included in the SAEs table) within any subsets of the clinical study, grouped by organ system, with number and frequency of such events in each arm/group of the clinical study.
- ADEs: this category indicates the anticipated device-related adverse events which may be related to the digital stethoscope AS-101.

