10.1 Adverse Events

The following list describes the common adverse events of procedural sedation (Non-ADE) and the device-related adverse event (ADE) to be recorded in this study.

| Patient Problems | ADE | non- ADE | Definition | |
|------------------------------|-----|-------------|--|---|
| Hypotension | - | AE | Decline for more than 30% from the Baseline over 1minutes | * |
| Bradycardia | - | AE | HR < 50 BPM | * |
| Tachycardia | - | AE | HR > 120 BPM | * |
| Hypoxemia | - | AE | Hypoxemia < 85 mmHg | 0 |
| Minor oxygen desaturation | - | - | SPO ₂ < 94 Not reported | |
| Moderate oxygen desaturation | - | AE | SPO ₂ < 90 | * |
| Severe oxygen desaturation | - | AE | SPO ₂ < 80 | * |
| Hypertension | - | AE | Reach 30% over the baseline for more than 1mintutes | * |
| Apnea(not prolonged) | - | - | Apnea 15-30 second | * |
| Apnea(long) | - | AE | Apnea > 30 second | * |
| AW obstruction | - | AE | | |
| Seizure | - | AE | | * |
| Failed sedation | - | - | | |
| Allergy | - | AE | | |
| Cardiovasular collapse | - | SAE | | |

Evaluating the Non-Inferiority of Airmod to Capnostream[™]35 on Respiratory Rate Monitoring and User Experience Clinical Evaluation

| Cardiac arrest | - | SAE | | |
|---|-----|-----|--|------------------|
| Myocardial infarction | - | SAE | | |
| Aspiration Pneumonia | - | SAE | | \bigtriangleup |
| Prolonged Cognitive Dysfunction (> 6month) | - | SAE | | \bigtriangleup |
| Encephalopathy | - | SAE | | \bigtriangleup |
| Skin irritated allergic dermatitis | AE | - | | |
| Skin irritation related allergenic shock | SAE | | | |
| | | | Red color is indicating "report to the IRB in a timely fashion". | |
| REF: https://www.ncbi.nlm.nih.gov/pmc/articles/PMC5836671/ | | | * Not include Transient Event (< 1mins) | |
| REF: https://pubmed.ncbi.nlm.nih.gov/27126387/ | | | riangle could lead to elongation hospital stay | |
| | | | O Hard to measurement | |

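### The only safety endpoint is zero observed USADEs, with no confidence limit and no account of anticipated serious device effects (minor)

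*SAP*

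**What the plan says.** Endpoint 5 reads the same in the Protocol synopsis, Protocol section 3 and SAP 4.4: "The absence of unanticipated serious adverse device effect (USADE) during study period and the questionnaire". No rate, limit or confidence level goes with it. SAP 4.3 and the synopsis give the overall aim as demonstrating non-inferiority in safety as well as performance; the fifth secondary objective is the softer one of evaluating safety and usability.

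Protocol 9.4.4 and SAP section 10 plan descriptive statistics: numbers of AEs and SAEs, numbers and percentages of patients affected, and tables by intensity and relationship to the product. SAP section 10 adds tables of deaths, of SAEs (anticipated and unanticipated) and of other AEs. It also sets up an ADE category and says that "this category indicates the anticipated device-related adverse events which may be related to the digital stethoscope AS-101". In the SAP 10.1 table, "Skin irritation related allergenic shock" stands in the ADE column and is graded SAE.

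On the denominator, SAP 5.1 gives the planned size: "In the total of 300 subjects enrolled at the OR and NOR area in the hospital". SAP 7.2 defines the Safety population as "All subjects who are enrolled in the study". SAP section 10 describes it as "All candidates who were subjected to the device with Airmod" and the comparator, that is, those on whom the devices were used.

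**The concern.** Two things are missing from an endpoint stated as absence.

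The first is a measure of how much the zero is worth. Zero events in a small group is compatible with a rate that matters; only the number of subjects and a confidence limit show how far the rate has been bounded. The plan supplies neither, although it attaches a 95% CI to the accuracy target in endpoint 1. Both devices are on every subject at once, so there is no separate control group to compare with. An observed zero could then be read as safety demonstrated.

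The second is coverage. The endpoint counts only unanticipated effects. A serious device effect that the SAP itself foresees could occur, and the endpoint would still be met. At stake is the wording of the safety conclusion, not the primary result.

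**Working it through.** The plan states no event rate, acceptable rate, confidence level or sample size for safety, so it has no safety figure to reproduce. The true rates below are assumptions, shown as a range.

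**Input.** n = 300 (SAP 5.1; all enrolled subjects count under SAP 7.2).

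**Chance of seeing no event.** P(0) = (1 − p)^n, with p the true proportion of subjects with a USADE.

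| Assumed true rate p | Calculation | P(0 of 300) |
|---|---|---|
| 1% | 0.99^300 | 4.9% |
| 0.5% | 0.995^300 | 22.2% (1 in 4.5) |
| 0.3% | 0.997^300 | 41% |
| 0.1% | 0.999^300 | 74.1% |

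**Exact (Clopper-Pearson) upper limit after zero events.** U = 1 − a^(1/n), with a the one-sided error.

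- a = 0.05: 1 − 0.05^(1/300) = 0.99%. The rule of three agrees: 3/300 = 1.00%.
- a = 0.025: 1 − 0.025^(1/300) = 1.22%.

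**Sensitivity to the SAP's dropout figure.** SAP Table 6 has "dropout rate=0.3", in percent, so 300 × 0.997 ≈ 299. At 299, P(0) at a true rate of 0.5% is 22.3%, and the limits are 1.00% and 1.23%. Nothing material changes.

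**Which events count.** No arithmetic is needed, only the SAP's own classification:

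1. SAP 10.1 lists the allergic shock in the ADE column and grades it SAE, so it is a serious device effect.
2. SAP section 10 defines the ADE category as anticipated.
3. Endpoint 5 concerns unanticipated serious device effects.
4. One such shock would therefore appear in the tables (1/300 = 0.33% of subjects), yet endpoint 5 would be met.

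It follows that the limits above, applied to endpoint 5 as it stands, bound the USADE rate only. They do not bound the rate of all serious device effects.

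**The case against.** The strongest reply is that endpoint 5 is not a formal test. It is the last secondary endpoint, is shared with a questionnaire, and has no hypothesis, alpha or success threshold beyond the word absence. Affected patients and percentages will be reported, and any reader of 0/300 can derive the limit. This stands, and it is why the point is minor. It does not remove the mismatch with an overall objective that speaks of demonstrating safety.

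On coverage, leaving anticipated effects out of an endpoint named for unanticipated ones is what the term means. A shock would not be lost: SAP section 10 tabulates anticipated and unanticipated SAEs, and SAP 7.5.3 obliges the DSMB to monitor device-related adverse events and allows for termination. This also stands. The gap is in the endpoint and the conclusion drawn from it, not in reporting or oversight.

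Four stronger readings are tempting, and the documents do not support them.

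- **That safety rests on 180 subjects.** Protocol 9.2 says "Considering a 40% withdrawal/dropout rate, we proposed a total enrollment of 300 subjects", and 300 × 0.6 = 180. That denominator needs every dropout to be unexposed. SAP 7.2 counts all enrolled subjects, several withdrawal reasons in Protocol 7.2 can arise after the sensor is in place, and SAP Table 6 gives 0.3%.
- **That safety is judged at 150 subjects.** SAP 7.5.1 ties early success at the interim analysis to the primary endpoint, SAP 7.5.3 applies no efficacy stopping rule, and the final analysis is at 300.
- **That 300 subjects cannot exclude 1 in 100.** This depends on the confidence level. At one-sided 97.5% the limit is 1.22% and 1% is not excluded; at one-sided 95% it is 0.99% and 1% is just excluded. The plan states no level for safety.
- **That the trial has a 1 in 5 chance of missing a real hazard.** The 22% belongs to an assumed rate of 0.5%. Over the range shown the figure runs from 4.9% to 74%.

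**Conclusion.** The point holds as a minor one. Endpoint 5 rests the safety conclusion on an observed zero with no limit, and one named serious device effect could occur without affecting it. After 0 USADE in 300, the most that can be said is that the USADE rate is below 0.99% (one-sided 95%) or 1.22% (one-sided 97.5%).

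This assumes that about 300 subjects are exposed and assessed, and that subjects are independent. The true rates in the table are illustrations only. Part of SAP 9.1 was not in the text I read; it concerns the primary endpoint, so a safety limit there is unlikely. The primary analysis is unaffected.

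**What to change.** In the Protocol synopsis, Protocol section 3 and SAP 4.4, restate the safety part of endpoint 5 as the number and proportion of subjects in the Safety population with any serious adverse device effect, anticipated or unanticipated, with USADE shown separately. In SAP section 10 and Protocol 9.4.4, add an exact Clopper-Pearson upper limit at a stated confidence level; one-sided 97.5% would match the one-sided alpha of 0.025 in SAP Table 6. Word the conclusion as the rate excluded, for example below 1.22% if 0 of 300, instead of absence. At the same time, reconcile the two descriptions of the Safety population (SAP 7.2 and SAP section 10), so that the denominator is fixed.

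The cost is wording in both documents and one exact interval. No new data are needed and trial conduct does not change. The price is a slightly less favourable safety statement.

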5.1 General Study Design and Plan

This is a prospective, multi-center, pivotal study. The purpose of this study is to evaluate the noninferiority of Airmod to Capnostream^{M35} for respiratory rate monitoring. In the total of 300 subjects enrolled at the OR and NOR area in the hospital, the interim analysis will be performed at the enrollment of 150 subjects during study period. (using OBrien-Fleming to determine α =0.00153) The target population is divided into non-anesthesia, and sedative anesthesia groups. The non-anesthesia group is proposed to enroll at least 40 patients in order to indicate normal patient population in the health care facilitate. The sedative and anesthesia groups will enroll up to 260 patients to cover a wide range of health condition, comorbidity and risk of sedative patients.

Subgroup analysis is planning to indicate the induction period, intraoperative period, and PACU period. And the body mass index (BMI) will be stratified by < 30 and \geq 30 (at least 30 Number) to further examine the high risk patients group. This study will not be randomized and blinded.

Safety will be assessed by the investigator(s) and will be monitored until the end of the study. All Adverse Events (AEs) and Serious Adverse Events (SAEs) occurring during the study period will be followed until the event is considered stable or until full resolution.

The duration of this study is estimated to be 12 months, while approximately 1.5 months for each individual subject to complete all participant visits.

5.2 Inclusion-Exclusion Criteria and General Study Population

(ICH E3;9.3. ICH E9;2.2.1)

Inclusion criteria:

- 1. Provision of signed and dated informed consent form.
- 2. Stated willingness to comply with all study procedures and availability for the duration of the study.
- 3. Male or female with at least 20 years of age.
- 4. Fit for intravenous general anesthesia (IVG) as assessed by pre-anesthesia evaluation.

Exclusion criteria:

- 1. Presence of neck pain or injuries.
- 2. Under the use of high-flow nasal cannula ventilation.
- 3. Unable to wear Airmod and Capnostream[™]35 device related accessories at the investigator's discretion.
- 4. As a vulnerable population, including legal incapacity or evidence that a subject cannot understand the purpose and risks of the study, regardless of authorized representative support.

5. Unwilling or unable to comply fully with study procedures (including non-toleration of the capnography cannula) due to any disease condition which can raise doubt about compliance and influencing the study outcome.

5.3 Randomization and Blinding

(ICH E3; 9.4.3, 9.4.6. ICH E9; 2.3.1, 2.3.2) This study will not be randomized and blinded.

5.4 Study Assessments

(ICH E3; 9.5.1. ICH E9; 2.2.2)

| Procedures | Screening ^a | Treatment ^a |
|-----------------------------------|------------------------|------------------------|
| Visit Number | 1 | 2 |
| Visit Days | -28 ~ 1 | 1 |
| Allowed visit window (days) | | +14 |
| Informed consent | х | |
| Criteria evaluation | х | |
| Medical history | х | |
| Demographic data ^b | х | |
| Physical examination ^c | х | |
| Vital signs ^d | х | |
| Study intervention administration | | X e |
| PAR assessment ^f | | X g |
| PADSS assessment ^f | | X g |

| AE review and evaluation | х |
|--|---|
| Concerning and the state of the | |

- a. Screening and treatment can be the same day.b. Demographic data include date of birth and gender.
- c. Physical examination includes general appearance, weight and height, HEENT (head, eyes, ears, nose, and throat), mouth, skin, neck (including thyroid), lymph nodes, spine, cardiovascular system, respiratory system, gastro-intestinal system, nervous system, musculoskeletal system, blood and blood forming organs, mental status, and other body systems if applicable.
- d. Vital signs include body temperature, sitting blood pressure and pulse rate.
- e. The administered anesthetic medication and dosage, surgery type, start and stop time of surgery will also be collected.
- f. Post Anesthetic Recovery (PAR) and Post Anesthetic Discharge Scoring System (PADSS) will be assessed upon admission and every 15 minutes after transferring to post anesthesia care unit (PACU).
- g. Subject will be discharged when PAR or PADSS score \geq 9, consider as complete the study.

Table 2. Study assessments

6 Sample Size

(ICH E3; 9.7.2. ICH E9; 3.5)

By referencing predicate device clinical trials on respiratory rate monitoring in the hospital setting, most of the cases recruited 120+ patients. In order to cover a wide range of health conditions, comorbidity, and risk, we proposed to enroll at least 40 non-anesthesia patients and up to 260 sedative / anesthesia patients from pre-anesthesia evaluation clinics (in a total of 300).

| Location | Preanesthesia Evaluation | Preprocedural Patient Preparation | Sedative/Analgesic medication induction | Intraoperation | Post anesthesia care unit (PACU) |
|--------------------|-----------------------------|--|--|----------------|--|
| OR | Enrollment | Device installation / Preparation | Trial period ^{1*} | Trial period | Trial period²* |
| NORA | Enrollment | Device installation / Preparation | Trial period ^{1*} | Trial period | Trial period² [*] |
| Location | Preanesthesia Evaluation | Non-anesthesia state | | | Eligible to discharge |
| Prep room, PACU | Enrollment (40) | Device installation and Trial period for 15~30 minutes | | | Device installation and Trial period for 15~30 minutes |

1* Notice : We included sedative/analgesic medical intended for general anesthesia and not intended for general anesthesia.

2° Notice : We followed the guidance that Patients receiving moderate procedural sedation may continue to be at risk for developing complications after their procedure is completed. Slow drug elimination may contribute to residual sedation and cardiorespiratory depression during the recovery period. Therefore, we proposed to track the recording until patient for fill the discharge requirement.

Fig 1. Enrollment plan of subjects

7 General Analysis Considerations

